### 1.2 KM-819

KM-819 is an innovative new drug that protects neuron cells from death through inhibition of the function of Fas (TNFRSF6)-associated factor 1 (FAF1), a cell death inducing protein in dopamine neuron cells.

It has been reported that the expression of FAF1 is increased in Parkinson's patient's brain tissue. Animal models relevant to Parkinson's disease have confirmed a significant increase of FAF1 in the midbrain. Parkinson's disease cell and animal models have confirmed an inhibition of cell death when FAF1 expression is reduced. Therefore, FAF1 is validated as a potential novel target for new drug discovery for Parkinson's disease. KM-819 has been developed as a compound targeting FAF1 as a therapy drug for Parkinson's disease.

KM-819 not only protects dopaminergic neuron cell from death (neuroprotection), but may also improve behavior similar to other drugs. Therefore, if KM-819 becomes successful as a new drug, it is expected to replace the current market and create new market by fulfilling unmet medical needs.

### **1.2.1 Non-clinical Data**

#### **1.2.1.1 Pharmacology**

KM-819 is a drug candidate with EC50 value of nM range for in vitro cell death protection assay study (in human neuronal cell line 200.3 nM and rat primary neuron 134.5 nM), and confirmed to exhibit dopaminergic neuron cell protection in 1-methyl-4-phenyl-1,2,3,6-tetrahydropyridine (MPTP)-induced Parkinson's disease animal models, and to have a superior neuron cell protection effects and the similar behavioral improvement effects compared to L-dopa. In addition, it demonstrates specific binding to the target protein FAF1 upon cell death related to Parkinson's disease.

In vitro efficacy of the FAF1 inhibitor KM-819 in Parkinson's disease cell model was evaluated using dopaminergic neuron cells obtained from rat substantia nigra. The cells treated with KM-819 showed better protection from death to MPTP compared to untreated cells in a dose-dependent manner (0.1, 1, and 10 uM).

Inhibitory effect of KM-819 on FAF1 signaling in Parkinson's disease cell model was evaluated using the human neuroblast cell line SH-SY5Y. Treatment with KM-819 inhibited the interaction of FAF1 with Caspase-8 and JNK1, 2 downstream targets of FAF1, in Parkinson's disease cell model induced by H2O2, and the subsequent studies done by Western blotting gave results that the drug inhibited the activation of Caspase-8 and JNK1 from 100 nM to 10 uM in a dose-dependent manner.

In acute Parkinson's disease models induced by MPTP in vivo, treatment with KM-819 at 20 mg/kg for 6 consecutive days orally protected dopaminergic neuron cells both in substantia nigra and striatum, compared to non-treated controls, and also improved the behavioral impairments in these models. These effects were dose-dependent at 1, 10, and 20 mg/kg.

In sub-acute Parkinson's disease models induced by MPTP, the effects of KM-819 were compared to a current Parkinson's disease drug L-dopa. Treatment with KM-819 at 20 mg/kg for 6 consecutive days orally protected dopaminergic neuron cells better than treatment with L-dopa which was injected into abdominal cavity at 20 mg/kg. And the improvement of behavior was very similar in these 2 groups. The effects of KM-819 on neuron cells in brain was also studied by MRI imaging and compared with a current Parkinson's disease drug ropinirole. Treatment with KM-819 for one week orally gave results in higher Fractional Anisotropy (FA) value from KM-819 than ropinirole, demonstrating the superior cell protection effects of KM-819 compared with ropinirole. Also, detecting dopamine transporters (DAT) scanning data by positron emission tomography (PET) imaging showed that both KM-819 and ropinirole treatments gave the higher Standardized Update Value (SUV) compared to non-treated controls, demonstrating the protective effects in dopaminergic neuron cells in striatum.

In chronic Parkinson's disease models induced by MPTP, pre- or post-treatment with KM-819 at 30 mg/kg for 3 months orally protected dopaminergic neuron cells both in substantia nigra and striatum, compared to non-treated controls.

Therefore, the efficacy of KM-819 in the protection of cell protection and behavior improvement were found in both in vitro and in vivo Parkinson's disease animal models.

#### **1.2.1.2 Safety Pharmacology**

Safety of KM-819 on various organs was evaluated by core battery of safety pharmacology tests. No changes in various neuronal behaviors and body temperature at up to 1000 mg/kg of KM-819

in male and female rats were observed. No changes in heart rate, blood pressure (BP), and electrocardiogram (ECG) variables including QT intervals at up to 500 mg/kg per oral (PO) dose in male dogs were observed. KM-819 did not inhibit the human ether-a-go-go related gene (hERG potassium channel) at up to 10 uM. KM-819 did not inhibit any respiratory functions in rats at up to 1000 mg/kg PO dose.

#### *1.2.1.3 Pharmacokinetics*

A pharmacokinetic (PK) study in male rats, by administering single intravenous (IV) injection of 5 mg/kg KM-819 showed:  $C_{max}$ : 62.73 ug/ml,  $t_{max}$ : 0.083 hr, and  $t_{1/2}$ : 7.08 hr. Single dose oral administration of 5 mg/kg KM-819 resulted in:  $C_{max}$ : 3.89 ug/ml,  $t_{max}$ : 3 hr, and  $t_{1/2}$ : 6.06 hr. Oral bioavailability assessed by comparing  $AUC_{0-\infty}$  for oral and IV administration was 35.97%.

A PK study in male dogs, by administering single IV injection of 1 mg/kg KM-819 showed:  $t_{max}$ : 0.08 hr,  $C_{max}$ : 11.91 ug/ml, and  $t_{1/2}$ : 8.61 hr. Single dose oral administration of 5 mg/kg and 10 mg/kg KM-819 resulted in:  $t_{max}$ : 0.83 hr and 0.58 hr,  $C_{max}$ : 6.01 ug/ml and 9.48 ug/ml, and  $t_{1/2}$ : 4.96 hr and 5.03 hr, bioavailability: 32.3% and 28.9%, respectively.

In vitro plasma protein binding is 99.96 %, 99.79%, and 99.96% in rat, dog and human, respectively. KM-819 at 10 uM did not inhibit CYP450s (including 1A2, 2C9, 2C19, 2D6, 3A4) and P-gp.

#### *1.2.1.4 Toxicology*

Toxicity of KM-819 was evaluated in rats (up to 28 days) and dogs (up to 14 days) by single and multiple PO dose. The toxicity was also tested by single IV injection in rats.

Repeated dose toxicity test in rats and dogs did not reveal any drug-related pathological tissue changes (including reproductive organ) or significant clinical symptoms at tested highest dose.

Single dose toxicity test in SD rats with oral doses of KM-819 at 500, 1000, and 2000 mg/kg did not result in any death, change in clinical observations, body weight, or biopsy results. Therefore, the approximate lethal dose (ALD) is above 2000 mg/kg. And from the test of KM-819 for 4 week repeated oral dose (2 weeks recovery) in SD rats, No Observed Adverse Effect Level (NOAEL) is 500 mg/kg/day.

Single IV injection of KM-819 at 25, 50, and 100 mg/kg did not result in any death, change in clinical observations, BW change, or biopsy results in SD rats.

In beagle dogs, single oral doses of KM-819 at 500, 1000, and 2000 mg/kg did not result in any death, or changes in clinical observations, body weight, or biopsy results except contamination of test materials in feces, therefore, the ALD is above 2000 mg/kg/day. During a 2-Week repeated dose study in male and female Beagle dogs (with 1 week recovery), KM-819 at 50, 250, and 1000 mg/kg did not result in any death, or changes in clinical observations, body weight, or biopsy results except contamination of test materials in feces. Liver damage (higher ALT, ALP, GGT, and enlargement in common bile duct in liver) was reported in one male dog following multiple dosing at 2000 mg/kg for 7 days. Therefore, NOAEL is 1000 mg/kg/day for both male and female Beagle dogs.

KM-819 did not show any genotoxicity from mutation reversion test, chromosome abnormality test, and bone marrow micronucleus test.

#### *1.2.2 Clinical Data*

KM-819 has not been investigated in humans yet, therefore, no clinical study data is available.

### **1.3 Rationale**

KM-819 has not previously been administered to humans. This First-in-Human study is therefore designed to provide safety, tolerability, PK, and pharmacodynamic (PD) data of KM-819 in healthy young adult male and elderly male or female subjects following ascending single and multiple dose administration. Data from this study will be used to guide rational drug dosing and therapeutic regimen choices in subsequent clinical studies.

### **1.4 Risk-Benefit Assessment**

Given the favorable toxicity profile and the positive results of in vitro and animal models, it is suggested that the present clinical study has an acceptable risk-benefit ratio.

The safety monitoring practices employed by this protocol are standard for a First-in-Human, single and multiple ascending dose study and are considered adequate to protect the subjects' safety. Subjects will be admitted to the Clinical Study Unit, where they will be monitored to detect adverse events (AE)s during the study and followed appropriately to ensure resolution of AEs. Sentinel dosing will be employed within each single dose cohort, and available safety and PK data will be assessed after each dose level to determine if it is safe to escalate the dose.

Subjects participating in this study will not benefit from administration of KM-819. None of the findings in non-clinical safety pharmacology or toxicology studies precludes further development of KM-819 in Phase 1 First-in-Human clinical trials.

## **2 STUDY OBJECTIVES**

### **2.1 Primary Objective**

- To evaluate the safety and tolerability of single and multiple ascending oral doses of KM-819 in healthy young adult male subjects.

### **2.2 Secondary Objectives**

- To evaluate the pharmacokinetics and pharmacodynamics of single and multiple ascending oral doses of KM-819 in healthy young adult male subjects.
- To evaluate the safety and tolerability of single and multiple oral doses of KM-819 in elderly male or post-menopausal female subjects.
- To evaluate the PK and PD of single and multiple oral doses of KM-819 in elderly male or post-menopausal female subjects.

### 3 OVERALL DESIGN AND PLAN OF THE STUDY

#### 3.1 Overview

This is a first-in-human, single-center, randomized, placebo-controlled, double-blind, sequential group Phase 1 study in healthy subjects. The aim of this study is to evaluate the safety, tolerability, PK, and PD following the escalation of single and multiple doses of KM-819.

The study will consist of 2 parts (Part A and Part B).

- Part A includes up to 5 cohorts of healthy young adult male subjects receiving single ascending doses (SAD)s of KM-819, and 1 additional single-dose cohort of elderly male or post-menopausal female subjects.
- Part B includes up to 4 cohorts of healthy young adult male subjects receiving multiple ascending doses (MAD)s of KM-819, and 1 additional multiple-dose cohort of elderly male or post-menopausal female subjects.

Dose escalation to the next level will be determined using the safety, tolerability, and PK data of the previous cohort.

#### Part A, Single Ascending Dose (SAD)

Up to 40 healthy young adult male subjects and 8 healthy elderly male or post-menopausal female subjects will be enrolled and randomized to receive either KM-819 or placebo.

Each of the 5 dose escalation cohorts consists of 8 healthy young adult male subjects; 6 subjects will receive single dose of 10, 30, 100, 200, or 400 mg KM-819 and 2 subjects will receive placebo.

Cohorts will be dosed sequentially with escalating doses, escalation to the next dose level will take place only after the safety, tolerability data, and available PK data from the previously treated dose cohort has been reviewed; see Section 3.4 for dose escalation criteria. In each of the 5 single dose cohorts, dosing of subjects will be sentinel, i.e., 2 subjects will be dosed on the first day (1 subject will receive active treatment and 1 subject will receive placebo) and the remaining 6 subjects will be dosed at least 24 hours after the first 2 subjects.

After completion of the 5 dose escalation cohorts, 8 elderly male or post-menopausal female subjects will be enrolled into an additional cohort; 6 subjects will receive 200 mg KM-819 and 2 subjects will receive placebo.

[figure not shown]
See Table 3-1 for Part A dose groups.

**Table 3-1: Dose Groups for Part A**

KM-819 Dose (mg)	Subjects on KM-819 (n)	Subjects on Placebo (n)	Total Subjects in Group (n)	Age Group
10†	6	2	8	Young adult male subjects
30†	6	2	8	
100†	6	2	8	
200†	6	2	8	
400†	6	2	8	
200	6	2	8	Elderly male or post-menopausal female subjects

† Doses between the current planned range may be assigned or a dose may be repeated depending on safety, tolerability, and pharmacokinetic data from previous subjects and cohorts.

All subjects will undergo a Screening period of up to 28 days and a 3-day Confinement period when they are hospitalized for study activities (Day -1 to Day 3). Subjects are required to return for outpatient visits on Day 4, Day 7, and for Follow-up Visit on Day 14. See Figure 3-1 for Part A SAD study design.

\*: Baseline

\*\*: Randomization and study drug administration

**Figure 3-1: Part A Single Ascending Dose Study Design**

**Part B, Multiple Ascending Dose (MAD)**

Part B will be conducted after completion of all cohorts of young adult male subjects in Part A. Up to 32 healthy young adult male subjects and 8 healthy elderly male or post-menopausal female subjects will be enrolled and randomized to receive either KM-819 or placebo.

Each of the 4 dose escalation cohorts will consist of 8 healthy young adult male subjects; 6 subjects will receive 30, 100, 200, or 400 mg of KM-819 once a day (QD) for 7 days and 2 subjects will receive placebo. Cohorts will be dosed sequentially with escalating doses.

After completion of the 4 dose escalation cohorts, 8 elderly male or post-menopausal female subjects will be enrolled into an additional cohort; 6 subjects will receive 200 mg KM-819 QD for 7 days and 2 subjects will receive placebo.

[figure not shown]
See Table 3-2 for Part B dose groups.

**Table 3-2: Dose Groups for Part B**

KM-819 Dose (mg)	Subjects on KM-819 (n)	Subjects on placebo (n)	Total Subjects in Group (n)	Age Group
30†	6	2	8	Young adult male subjects
100†	6	2	8	
200†	6	2	8	
400†	6	2	8	
200	6	2	8	Elderly male or post-menopausal female subjects

† Doses between the current planned range may be assigned depending on safety, tolerability, and pharmacokinetic data from previous subjects and cohorts.

All subjects will undergo a Screening period of up to 28 days and an 8-day Confinement period when they are hospitalized for study activities (Day -1 to Day 8). Subjects are required to return for a Follow-up Visit on Day 14. See Figure 3-2 for Part B MAD study design.

**Figure 3-2: Part B Multiple Ascending Dose Study Design**

### 3.2 Criteria for Evaluation of the Study

The study involves safety, PK, and PD assessments. The specific endpoints are listed below.

#### 3.2.1 Safety Endpoints

##### Parts A and B

- Reporting AEs (nature, frequency, severity, time of onset/offset)
- Standard clinical laboratory evaluations
- Vital signs measurements (tympanic temperature, supine pulse, and supine BP)
- 12-lead ECGs

#### 3.2.2 Pharmacokinetic Endpoints

##### KM-819

Plasma PK parameters for KM-819 include the following for single dose and/or multiple dose analysis:

##### Single Dose and Day 1 of multiple doses

- $AUC_{last}$ : area under the plasma concentration-time from predose (time 0) to the last quantifiable concentration
- $AUC_{inf}$ : area under the plasma concentration-time curve from predose (time 0) extrapolated to infinity
- $AUC_{inf}(\%)_{extrap}$ : Percentage of  $AUC_{inf}$  that is due to extrapolation beyond  $t_{last}$
- $CL/F$ : apparent oral clearance
- $C_{max}$ : maximum plasma concentration determined directly from the concentration-time profile
- $\lambda_z$ : terminal elimination rate constant
- $t_{1/2}$ : apparent terminal elimination half-life
- $t_{lag}$ : lag time

- $t_{max}$ : time to achieve maximum observed plasma concentration determined directly from the concentration-time profile
- $V_z/F$ : volume of distribution
- Other parameters, as appropriate, including dose-adjusted parameters.

Day 7 of multiple doses

- $AUC_{tau}$ : area under the plasma concentration-time curve for a dosing interval
- $AUC_{last}$ : area under the plasma concentration-time from predose (time 0) to the last quantifiable concentration
- $CL/F$ : apparent oral clearance
- $C_{max}$ : maximum plasma concentration determined directly from the concentration-time profile
- $C_{min}$ : minimum plasma concentration determined directly from the concentration-time profile
- $C_{trough}$ : observed plasma concentration before dosing
- $R_{ac}(AUC)$ : observed accumulation by  $AUC$
- $R_{ac}(C_{max})$ : observed accumulation by  $C_{max}$
- $t_{lag}$ : lag time
- $t_{max}$ : time to achieve maximum observed plasma concentration determined directly from the concentration-time profile
- $V_z/F$ : volume of distribution
- Other parameters, as appropriate, including dose-adjusted parameters

Cerebrospinal fluid (CSF) PK parameter for KM-819 includes the following after multiple dose CSF sample collection:

- KM-819 concentration in CSF

### ***3.2.3 Pharmacodynamic Endpoints***

In both Parts A and B, mean and absolute value change from baseline at each post-baseline measurements for:

- Bond and Lader Visual Analogue Scale (VAS)
- Profile of Mood States (POMS)
- Korean Wechsler Adult Intelligence Scale-IV (K-WAIS-IV)
- C-SSRS

In Part B only, PD parameters in plasma and CSF including:

- alpha synuclein oligomer
- total Tau
- phospho-Tau
- ratio of CSF concentration/Plasma  $C_{max}$

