### **3.4 Dose Escalation Criteria**

In Part A, escalation to the next dose level will take place only after the safety and tolerability data for all subjects in the cohort (through Day 4) and available plasma PK data (through the 72-hour sample postdose) from the previously administered dose cohort has been reviewed. Data from exploratory PD assessments and CNS scales will not be included in the review for dose escalation decisions. Within the planned dose range a dose lower than the next planned dose level may be tested, depending on the emerging safety, tolerability, and/or other relevant data (e.g., plasma PK data).

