### 4.2 Exclusion Criteria

Subjects will be entered into this study only if they meet none of the following criteria:

1. Subject has a known or suspected hypersensitivity to KM-819, or any components of the formulation(s) used.
2. Subject has previously participated in a clinical study with KM-819.

3. Subject has any of the liver enzymes (aspartate aminotransferase [AST], alanine transaminase [ALT], alkaline phosphatase,  $\gamma$ -glutamyl transferase) or total bilirubin (TBIL) above the ULN. If any liver enzyme is  $> 1 \times$  ULN but  $< 1.5 \times$  ULN, the assessment may be repeated once during the Screening period or on check-in. If the repeated assessment is above the ULN, it is exclusionary. If the initial value is  $> 1.5 \times$  ULN, it cannot be repeated and is exclusionary.
4. Subject has any clinically significant history of allergic conditions (including drug allergies, asthma, eczema, or anaphylactic reactions, but excluding untreated, allergic rhinitis or rhino-conjunctivitis, or house dust mite allergy at time of dosing).
5. Subject with a history of a suicide attempt or suicidal behavior. Any recent suicidal ideation (a level of 4 or 5) within the last 3 months, or having a positive C-SSRS at check-in (Day -1), or who is at significant risk to commit suicide, as judged by the Investigator using the C-SSRS at Screening.
6. Subject has/had febrile illness or symptomatic viral, bacterial (including upper respiratory infection) or fungal (non-cutaneous) infection within 1 week before site check-in.
7. Subject has any clinically significant abnormality following the Investigator's review of the physical examination, ECG, and protocol-defined clinical laboratory tests at Screening or site check-in.
8. Subject has a mean pulse  $< 40$  or  $> 90$  beats per minute (bpm); mean systolic blood pressure (SBP)  $> 140$  mmHg; or mean diastolic blood pressure (DBP)  $> 90$  mmHg (measurements taken in triplicate after subject has been resting in the supine position for 5 minutes; pulse will be measured automatically) at Screening or check-in. If the mean pulse, mean SBP, or mean DBP is out of the range specified above, 1 additional triplicate measurement may be taken at Screening and check-in.

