#### 4.3 Subject Withdrawal and Replacement

A subject may withdraw from the study at any time without penalty and for any reason without prejudice to his/her future medical care. Participation of subjects may also be discontinued based on the medical judgment of the PI in conjunction with the Sponsor for any of the following reasons:

- ECG abnormalities:  
Any increases in QTcF > 500 msec or increase > 60 msec from baseline as confirmed with 3 consecutive ECGs taken within 5 minutes, with at least a 1-minute interval.
- Suicidality:  
Any suicide attempt or any recent suicidal ideation (a level of 4 or 5) since the last assessment, or a significant risk to commit suicide, as judged by the PI using the C-SSRS.
- Liver Safety Monitoring:  
Please refer to Stopping Criteria No. [2](#).
- After enrolment, the subject is found to violate the inclusion and/or exclusion criteria
- AE(s)
- Subject lost to follow-up
- Major protocol violation
- Use of prohibited medications mentioned in Section [5.8](#)
- The Investigator may, after discussion with the subject, withdraw the subject due to any serious safety concerns
- The study is terminated prematurely
- Other

In all cases, the reason(s) for withdrawal, and the primary reason, must be recorded on the electronic case report form (eCRF). Subjects who are withdrawn will have an Early Discontinuation (ED) Visit per the Schedules of Assessments (see Table [7-1](#) and Table [7-2](#)).

A subject may also be withdrawn from study by the Sponsor, Regulatory Authorities, or IECs/IRBs.

Subjects will also be withdrawn if the entire study is terminated prematurely as described in Section [9.10](#).

Withdrawn subjects may be replaced at the discretion of the Sponsor with agreement of the Investigator. Subjects who are discontinued because of treatment-emergent AE (TEAE) or possible toxic effects of the drug will not be replaced.

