9. All hematology and serum chemistry labs will be taken after fasting for a minimum of 8 hours.
10. Plasma samples for pharmacokinetics of KM-819 will be obtained on Day 1 predose (within 30 minutes prior

---

to study drug administration) and 0.25, 0.5, 1, 2, 4, 6, 8, 12, 24, 48, and 72 hours postdose.

11. Urine samples will be taken at: Day 1 predose (within 1 hour before study drug administration) and from 0 to 24 hours postdose.
12. Bond and Lader VAS, POMS, and K-WAIS-IV will be performed on Day -1, Day 1 (predose) and at 3, 6, 12, 24, 48, and 72 hours postdose ( $\pm$  30 minutes for each time point).
13. The version of the C-SSRS to be performed at Screening is the “Baseline-Screening for Phase 1,” and the version of the C-SSRS to be performed on Day 3 (or at ED) is the “Since Last Visit”.

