6. Screening height and weight will be used for BMI calculation for assessment of eligibility.
7. Blood will be tested for HBsAg, anti-HAV IgM, anti-HCV Ab, and anti-HIV Ab.
8. All hematology and serum chemistry labs will be taken after fasting for a minimum of 8 hours.
9. Simple spine X-ray examination will only be conducted at Screening for healthy elderly cohort.
10. Plasma samples for pharmacokinetics of KM-819 will be obtained on Day 1 predose (within 30 minutes prior to study drug administration) and 0.25, 0.5, 1, 2, 4, 6, 8, and 12 hours postdose, predose on Days 2, 3, 4, 5, 6,

---

and on Day 7 predose (within 30 minutes prior to study drug administration) and 0.25, 0.5, 1, 2, 4, 6, 8, 12, and 24 hours postdose.

11. CSF samples for pharmacokinetic of KM-819 will be obtained on Day 1 (at -120 minutes to 0 minute prior to the first dosing) and on Day 7 (at 1 hour after last dosing).
12. CSF samples for pharmacodynamic of KM-819 will be obtained on Day 1 (at -120 minutes to 0 minute prior to the first dosing) and on Day 7 (at 1 hour after last dosing).
13. Plasma samples for pharmacodynamic of KM-819 will be obtained on Day 1 (within 30 minutes prior to study drug administration) and on Day 7 (at 1 hour after last dosing).
14. Bond and Lader VAS, POMS, and K-WAIS-IV will be performed on Day -1, on Day 1 and Day 7 at predose, 3, 6, 12, and 24 hours postdose ( $\pm$  30 minutes for each time point).
15. The version of the C-SSRS to be performed at Screening is the “Baseline-Screening for Phase 1,” and the version of the C-SSRS to be performed on Day 3 and Day 8 (or at ED) is the “Since Last Visit”.

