### 7.2.2 Visits for Part A Single Ascending Dose

#### 7.2.2.1 Confinement Visit (Visit 2)

Visit 2 for SAD will occur within 28 days after Screening.

On Day -1 (check-in), subjects will need to attend the study center, the following assessments will be performed:

- confirmation of inclusion/exclusion criteria
- concomitant medication
- assessment of AE
- vital signs measurement and physical examination
- ECG assessment
- hematology and biochemistry blood sampling
- urinalysis sampling

- urine drug/cotinine tests
- alcohol breath test
- scales assessment

All results necessary for evaluation of the inclusion and exclusion criteria must be available before determining whether or not the subject can continue in the study.

Once verified eligible to the study, the subjects will be required to stay in study center for 3 nights (confined from the evening of Day -1 to Day 3).

On Day 1, the procedures to be performed at predose are listed below:

- Randomization: eligible subjects will be randomized to receive either KM-819 or placebo
- vital signs measurement (predose)
- ECG assessment (predose)
- scales assessments (predose)
- Urine sampling within 1 hour before dosing
- PK blood sampling within 30 minutes before dosing

Study drug will be administered from 8:00 to 10:00.

The procedures to be performed at postdose are listed below:

- postdose PK blood sampling at 0.25, 0.5, 1, 2, 4, 6, 8, and 12 hours (see Table [7-1](#))
- postdose vital signs measurements at 0.5, 1, 2, and 4 hours
- postdose ECG assessment at 1 hour
- postdose urine sampling from 0 to 24 hours
- postdose scales assessments at 3, 6, and 12 hours

The following assessments will also be performed during Day 1:

- concomitant medication
- assessment of AE

On Day 2 to Day 3, the procedures to be performed are listed below:

- concomitant medication
- assessment of AE
- vital signs measurement
- ECG assessment (only on Day 2)
- hematology and biochemistry blood sampling (only on Day 2)
- urinalysis sampling (only on Day 2)
- postdose PK blood sampling at 24 hour and 48 hours
- postdose scales assessments at 24 hours and 48 hours
- physical examination (only on Day 3)
- C-SSRS assessment (only on Day 3)

Subjects will be allowed to leave the study center after completing all the procedures on Day 3.

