#### **7.2.4 Early Termination Visit**

Subjects who discontinue early from the study should, if possible, have an ED Visit. This visit should take place as soon as possible after the subject stops taking study drug/after it was learned that the subject will not be able to complete Follow-up. The observations and procedures scheduled for Day 3 (Part A, safety laboratory and ECG assessment also needed) or Day 8 (Part

B) should be performed at the ED Visit. For subjects who discontinue early from the study during out-patient period (i.e., after completion of hospitalization period), C-SSRS will not be done at ED visit. Scales (Bond and Lader VAS, POMS, and K-WAIS-IV) will not be assessed for all the early discontinued subjects.

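### The C-SSRS guides eligibility and withdrawal but is classed only as a PD endpoint, with an uninterpretable change from baseline and a Day -1 check missing from the schedule

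*Protocol*

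**What the plan says.** **Use in decisions.** Exclusion 5 (protocol 4.2) bars, among others, a subject "having a positive C-SSRS at check-in (Day -1"). Protocol 4.3 allows withdrawal for "Any suicide attempt or any recent suicidal ideation (a level of 4 or 5) since the last assessment", or for significant suicide risk as judged with the same instrument.

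**Classification.** Protocol 3.2.3 and SAP 6.3.13 list the C-SSRS with the Bond and Lader VAS, POMS and K-WAIS-IV under this PD definition: "In both Parts A and B, mean and absolute value change from baseline at each post-baseline measurements for" each of them. It is not among the safety endpoints (protocol 3.2.1) or the assessments on which SAP 6.3.15 bases safety.

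**Forms and timing.** Table 7-1, footnote 13: "The version of the C-SSRS to be performed at Screening is the" Baseline-Screening for Phase 1 version; on Day 3 it is Since Last Visit. For Part B, the "version of the C-SSRS to be performed on Day 3 and Day 8 (or at ED) is the" Since Last Visit version (Table 7-2, footnote 15).

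**Baseline.** The PD baseline sentence in SAP 6.3.13 sets Day 1 for the three scales and the biomarkers and does not mention the C-SSRS. The default in protocol 8.2 and SAP 6.3.1 is the last scheduled measurement before dosing.

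**Outputs.** Protocol 8.8 plans continuous and categorical descriptive statistics for the C-SSRS. SAP section 10 numbers two listings, 16.2.9.7.1 and 16.2.9.7.2, both on the PD population. SAP 6.3.13 says the PD listings will carry absolute values and changes from baseline. SAP section 8 contains no C-SSRS table.

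**The concern.** This is a first-in-human study with safety as its primary objective, and the C-SSRS is the instrument by which it screens for and acts on suicidality. Three things follow from treating it only as a PD scale.

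- The analysis asks for a quantity, change from baseline, that the form versions do not support.
- A check on which eligibility depends appears nowhere in the schedule. That also affects how a post-dose finding can be attributed to the drug.
- The only planned display uses an analysis set that can leave out dosed subjects.

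What is at stake is a C-SSRS finding below the withdrawal threshold that nobody records as an adverse event. It would have no usable summary, and in a few cases might not be displayed at all.

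**Working it through.** The plan gives no figure for the C-SSRS to reproduce. The check sets the texts side by side and counts the affected assessments.

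**1. Scheduled assessments** (protocol Tables 3-1, 3-2, 7-1 and 7-2; 6 active and 2 placebo per cohort).
- Part A: 6 cohorts × 8 = 48 subjects (36 active, 12 placebo), one post-dose C-SSRS each (Day 3): 48.
- Part B: 5 cohorts × 8 = 40 subjects (30 active, 10 placebo), two each (Days 3 and 8): 80.
- Post-dose total: 48 + 80 = 128. Active: 36 + 60 = 96. Placebo: 12 + 20 = 32.
- Pre-dose: 48 + 40 = 88 at Screening, 0 on Day -1.

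**2. What the change would compare.** With no C-SSRS-specific baseline, the default rule gives Screening. All 88 Screening forms are one version and all 128 post-dose forms are another, with a different recall period. SAP 6.1.4 describes the instrument but defines no score. A programmer could not derive the change without inventing a score, and the result would still mix two recall periods.

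**3. Is there a Day -1 C-SSRS?** Tables 7-1 and 7-2 have no Day -1 mark for it. The Day -1 lists in 7.2.2.1 and 7.2.3.1 include a scales assessment, but protocol 6.1.2 and 7.2.4 reserve that term for VAS, POMS and K-WAIS-IV: "Scales (Bond and Lader VAS, POMS, and K-WAIS-IV) will not be assessed for all the early discontinued subjects". The line "C-SSRS assessment (only on Day 3") sits in the Day 2 to Day 3 list, so it separates Day 3 from Day 2 and decides nothing about Day -1. The omission rests on the tables and the Day -1 lists.

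**4. Consequence for the Day 3 form.** Assume that Since Last Visit reaches back to the previous C-SSRS, and that there is no Day 0. Post-dose time to Day 3 is 2 days.

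| Previous C-SSRS | Pre-dose days | Post-dose share of window |
|---|---|---|
| Screening, Day -28 | 28 | 2/30 = 7% |
| Screening, Day -2 | 2 | 2/4 = 50% |
| Check-in, Day -1 | 1 | 2/3 = 67% |

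This concerns the 88 Day 3 forms. On the same assumption, the 40 Day 8 forms in Part B look back only to Day 3 and are wholly post-dose.

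**5. If a site does a Day -1 form to satisfy exclusion 5.** No version is named for it. The default baseline (last scheduled) still points to Screening, while the repeated-measurement rule in SAP 6.3.1 (last value obtained before dosing) points to Day -1.

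**6. Display.** There are two numbered listings on the PD population, no table, and nothing on the safety population. The PD set drops subjects with important deviations affecting PD (SAP 6.2.3). An early-discontinuation visit during confinement collects the C-SSRS but not the scales (protocol 7.2.4).

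**The case against.** The strongest reply is that little is lost. Four stronger readings are tempting, and the documents do not support them.

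- *The C-SSRS will be analysed only as a mean change.* Protocol 8.8 also provides for categorical statistics, SAP 6.3.1 promises frequency counts for qualitative variables, and no mean-change table is numbered. An individual result stays visible in the listing. This stands. What remains is that SAP 6.3.13 still requires a change value in the listing and no categories are defined.
- *There is no baseline.* If the schedule is followed, the default rule gives Screening. Doubt arises only when an unscheduled Day -1 form exists.
- *Suicidality could go unreported.* Adverse events must be documented whatever their source (protocol 6.4.1.2). Adverse events and withdrawals for suicidality are displayed on the safety population (SAP 6.3.8, 6.3.15.1). Loss from the PD set is also narrow. Protocol 8.8 and SAP 6.3.13 treat the C-SSRS as a PD parameter, and one such parameter may be enough for inclusion. The early-withdrawal route further needs a subject to leave before the first post-dose scales at 3 hours.
- *The C-SSRS is kept out of escalation review.* Protocol 3.4 states: "Data from exploratory PD assessments and CNS scales will not be included in the review for dose escalation decisions". But the protocol names the C-SSRS apart from the scales and never calls it exploratory, so exclusion is not shown.

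On Day -1, one can also argue that the site must obtain the result anyway. Both parts require eligibility to be confirmed that day with all necessary results in hand, and waivers are not granted. That is a fair reading, and if it is followed the long look-back disappears. It confirms, however, that the schedule omits something the protocol requires, and it leaves the form version and the baseline unsettled.

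**Conclusion.** The point holds in a limited form and should be corrected. The required change from baseline is not interpretable for any of the 128 scheduled post-dose assessments. An eligibility check that exclusion 5 relies on is missing from the schedules and Day -1 lists for all 88 planned subjects. Both listings use a population that could, in a few cases, omit a dosed subject.

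These counts describe scope, not harm. The documents give no rate for findings that fall below the withdrawal threshold and are not recorded as adverse events, so no number of missed cases can be stated. The look-back shares (7% to 50%, against 67%) hold only if no Day -1 form is done and the Day 3 form reaches back to Screening. The documents establish neither lost suicidality events nor exclusion of the C-SSRS from escalation decisions.

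**What to change.** 1. Add the C-SSRS on Day -1, with the form version named, to Tables 7-1 and 7-2 and to the Day -1 lists in 7.2.2.1 and 7.2.3.1. Name it in the SAP as the pre-dose reference.
2. Take the C-SSRS out of the change-from-baseline endpoints (protocol 3.2.3 and synopsis, SAP 6.3.13) and make it a safety variable (protocol 3.2.1, SAP 6.3.15).
3. Add one table per part, by dose and pooled placebo, counting subjects with any post-dose ideation (by level) or behaviour, and subjects new or worse than the pre-dose reference.
4. Produce Listings 16.2.9.7.1 and 16.2.9.7.2 on the safety population without a change value.
5. Optional clarification: one sentence in protocol 3.4 saying that available C-SSRS results belong to the safety data reviewed for escalation.

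The cost is wording, two small tables, a population change for two listings, and one short interview per subject: at most 88 for the planned subjects, before any replacements. Exclusion 5 already presupposes that interview, and no visit or subject is added.
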